18.0 Safety Analyses

18.1 Safety Variables

The following safety variables will be summarized:

- AEs
- Vital Signs
 - Supine Blood Pressure
 - Systolic Blood Pressure
 - Diastolic Blood Pressure
 - Pulse rate
 - Temperature
- Electrocardiograms (ECG)
 - Heart Rate
 - PR Interval
 - QRS-Duration
 - QT Interval
 - QTc (Fredericia) Interval
- Clinical Laboratory Evaluations
 - Clinical Chemistry
 - Hematology
 - Urinalysis

18.1.1 Adverse Events

All AE summaries will include only TEAEs. TEAEs are those which start or worsen relative to the pretreatment state after the first dose of study drug.

All AEs (including non-treatment-emergent events) will be listed, including the AE description (verbatim term), Medical Dictionary for Regulatory Activities (MedDRA) system organ class (SOC) and preferred term (PT), start date and time, end date and time, severity, relation to study drug, seriousness, action taken, and outcome.

TEAEs occurring following dosing in a specific period but before dosing in the next period will be attributed to that specific period. If the time is missing for an AE on a dosing day then the AE will be attributed to the treatment given on that day.

A breakdown of the number of events, number and percentage of subjects reporting TEAEs, categorized by SOC, PT and overall, coded according to MedDRA (Version 21.1 or latest version), will be presented by treatment and all active treatments combined and overall. This summary will be presented for all TEAEs and for TEAEs considered related to the study medication.

Additionally, a summary table with TEAEs by severity and relationship to study drug will be presented by study part and treatment.

The following missing data will be imputed as defined (for calculations only / will not be presented):

- Missing AE start and / or end times for the calculation of onset and duration will be assumed to be at 00:01 for a start time and 23:59 for end times
- Missing AE severity or relationship will be assumed to be severe or related, respectively
- Missing AE start times for the determination of treatment emergence will be assumed to occur after treatment unless partial date documents the AE as happening prior to treatment
- Missing AE start times for the determination of treatment assignment will be assumed to occur after treatment on the recorded date one minute after dosing
- Missing AE start date will be assumed to be after treatment for the determination of TEAE and on treatment for single treatment studies but will not be attributed to treatment in studies with multiple treatments

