5.2.1 Secondary Endpoints

- Treatment-emergent (TE) adverse events (AE), serious AEs.
- Decrease in CA-induced DBF relative to placebo measured by LSCI at 3 hours post-dose.
- Summary of LY3526318 plasma concentrations by dose and time point.

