6.0 Study Design

This is a Phase 1 randomized, double-blind, placebo-controlled, 4-way crossover study of LY3526318 in healthy female participants.

All participants will have 2 screening visits with the first to evaluate the health of the participant and the second visit to undergo an LDI assessment to ensure a response of at least 100% increase in DBF between pre- and post-CA challenge. Following a screening period of up to 28 days, eligible participants will be confined to the clinical research unit from Day 1 until all assessments are completed on Day 2 of each dosing period.

As summarized in [Table 1](#), each participant will be randomly assigned to 1 of 4 treatment sequences, with a ratio of 3 LY3526318: 1 placebo. Each participant will receive 3 doses of LY3526318 and 1 dose of placebo in a crossover manner, with at least 6 days of washout between doses. The planned dose levels of LY3526318 are anticipated not to exceed the maximum administered dose in the SAD portion of Study CVAA.

Table 1 Treatment Sequence

Sequence	N	Period 1	Period 2	Period 3	Period 4
P132	4	P	D1	D3	D2
12P3	4	D1	D2	P	D3
231P	4	D2	D3	D1	P
3P21	4	D3	P	D2	D1

During each visit (screening and study periods), each patient will undergo at least 30 minutes acclimatization and placement of 3 rubber O-rings on the volar surface of the forearm. Prior to study drug administration, a pre-drug DBF will be collected without CA. For each time point following study drug administration, pre-CA measurements will be performed for the areas defined by the rings within 10 minutes before CA application. After the pre-CA measurements, a 20 μ L topical dose of 10% CA will be applied in the proximal O-ring of the participant's forearm. Using the same procedure, a 20 μ L topical dose of 3% CA will be applied in the medial ring, followed by a 20 μ L topical dose of the vehicle solution to the distal ring. LDI/LSCI measurements will again be performed approximately 20 minutes after CA and vehicle applications. Specific details of the procedure will be agreed upon and documented between the sponsor and investigator and research staff operating the equipment.

All assessments will be performed as defined in Schedule of Activities ([Appendix 2: Schedule of Assessments](#)).

All participants will attend a safety follow-up visit about 7 days following the last dose of study drug.

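### SAP 18.1.1 makes every adverse event with no start date treatment-emergent but gives it no treatment, even where the end date shows it preceded dosing or leaves only Period 1

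*SAP*

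**What the plan says.** SAP 18.1.1 defines the event class and the usual attribution: "TEAEs are those which start or worsen relative to the pretreatment state after the first dose of study drug", and "TEAEs occurring following dosing in a specific period but before dosing in the next period will be attributed to that specific period". The main summaries "will be presented by treatment and all active treatments combined and overall".

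The section closes with a list of imputation rules. The last one reads in part "Missing AE start date will be assumed to be after treatment for the determination of TEAE". It then separates two kinds of study: with a single treatment the event is placed on treatment, but such an event "will not be attributed to treatment in studies with multiple treatments". SAP 6.0 describes a "4-way crossover study of LY3526318 in healthy female participants", so the second branch governs.

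That bullet has no exception. A neighbouring bullet, on missing start times, does have one: it yields where a partial date shows that the event came before treatment. The end date is collected, since the adverse event listing carries "start date and time, end date and time, severity, relation to study drug, seriousness, action taken, and outcome". SAP 5.2.1 names the secondary safety endpoint as "Treatment-emergent (TE) adverse events (AE), serious AEs".

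**The concern.** The rule fixes two things at once, emergence and attribution, and settles both without looking at dates that are already in the database. That can go wrong in two ways.

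- An event that was over before dosing can enter the treatment-emergent counts. Such events can occur: Protocol 9.2.1 has adverse events recorded from consent, screening lasts up to 28 days, and it includes a cinnamaldehyde challenge.
- An event that can belong to only one treatment period can be missing from that treatment's column.

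At stake is the accuracy of the by-treatment safety tables, which report a secondary endpoint. Protocol 10.3.1 promises event summaries by dose level and for placebo, and an unattributed event is in neither. The SAP does not say whether such events get a row, column or footnote of their own. The table by severity and relationship is described by study part and treatment with no overall column mentioned, so an unattributed event has no stated place there at all.

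**Working it through.** The plan gives no figure on this point, so there is nothing to reproduce. The check lists every case by where the end date falls.

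**Inputs.** Doses on Days 1, 15, 29 and 43 (Schedule of Activities). Sixteen participants, four per sequence (SAP Table 1). Percentages use participants exposed within a treatment (SAP 9.1.3).

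| Undated event ended | Start could lie in | Periods left once assumed treatment-emergent | Under SAP 18.1.1 as written | Result |
|---|---|---|---|---|
| Before the Day 1 dose | pre-dose only | none | treatment-emergent, no treatment | overall count too high |
| After the Day 1 dose, before the Day 15 dose | pre-dose, Period 1 | 1 | treatment-emergent, no treatment | Period 1 treatment too low; all-active too low if that treatment was active |
| Period 2 | pre-dose, Periods 1–2 | 2 | same | defensible |
| Period 3 | pre-dose, Periods 1–3 | 3 | same | defensible |
| Period 4 | pre-dose, Periods 1–4 | 4 | same | defensible |

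**Row 1.** An event that ended before the first dose can neither start nor worsen after it. It fails the definition in the same section, yet the last bullet admits it.

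**Row 2.** The SAP has already chosen to assume that the event began after treatment. On that assumption only Period 1 remains, and the sequence gives the treatment: placebo in P132, D1 in 12P3, D2 in 231P, D3 in 3P21. The ordinary attribution rule would place the event there; the last bullet does not.

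**Size.** With 16 exposed, one participant changes a cell by 1/16 = 6.25 percentage points, and two by 2/16 = 12.5 points. This is an upper limit for each participant: if she already has another event in the same cell, the percentage does not move and only the event count changes.

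**Example.** A participant on 12P3 has one undated event that ended on Day 5 and no other event of that kind. Using the end date, the D1 cell is 1/16 = 6.25%. As written it is 0/16, while overall is 1/16.

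**The case against.** The strongest reply is that the intent is already clear. The start-times bullet lets a partial date override the default, and the definition itself excludes an event that was over before dosing, so a careful programmer might do the right thing. This carries some weight as to intent. But the exception sits in a different bullet, refers to a partial date and not to the end date, and is not repeated for missing start dates. Followed literally, the last bullet gives the wrong result.

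A second reply is that an event ending in Period 1 may have begun in screening, so placing it in Period 1 is itself an assumption. True, but it is the SAP's own assumption. The point is only that the consequence should follow from it.

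A third reply concerns importance, and it stands. The summaries are descriptive. All adverse events are listed individually with recorded dates, and deaths, serious events and withdrawals due to events have their own outputs. Clinic visits on Days 8, 22 and 36 break up the outpatient stretches, with about 6 days from discharge on Day 2 to Day 8 and about 6 more to the next admission on Day 14, so few start dates should be lost.

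A reader might also infer stronger things that the documents do not support:

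- *The end date generally fixes the period.* It does so only before the second dose; afterwards it is just an upper bound.
- *The dose columns will look cleaner than placebo.* Unattributed events leave the placebo column too, and Table 1 gives each of the four treatments to four participants in Period 1. No direction is shown.
- *The treatment columns should add up to overall.* This holds for event counts only. In a crossover one participant can appear under several treatments.
- *The rule clashes with setting a missing relationship to related.* It does not. Relationship is a causality judgement made blind, and it does not identify a dose or placebo.

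**Conclusion.** The point holds in a narrow form. SAP 18.1.1 gives a wrong result in two identifiable cases: undated events that ended before the first dose, and undated events that ended after the first dose but before the second. In the first case the overall treatment-emergent count is too high. In the second the Period 1 treatment column is too low, as is the all-active column when that treatment was active. For later end dates, leaving the event unattributed is reasonable, unless a partial start date narrows the choice.

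This is a minor correction. The documents give no rate of missing start dates; 0 to 2 such events in the trial is an assumption. Each affected participant changes a 16-participant cell by at most 6.25 percentage points, and only if she has no other event in that cell. The primary pharmacodynamic analysis is not affected.

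**What to change.** Replace the last imputation bullet of SAP 18.1.1 with a rule that uses the end date and any known part of the start date before assuming anything:

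1. If these show that the event ended before the first dose, or started before it and did not worsen afterwards, it is not treatment-emergent.
2. Otherwise assume it is treatment-emergent. If only one treatment period is possible, attribute it to that period's treatment.
3. If more than one period remains possible, leave it unattributed and show it in a separate *treatment not determinable* row or footnote, so that event counts reconcile with the overall column.

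Where the end date falls on a dosing day and the end time is missing, the event has not been shown to end before that dose and should be handled on that basis.

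Counting an undated event under every treatment it might belong to is not recommended. One that ended in Period 4 could then appear in four columns, and event counts by treatment would exceed the overall count.

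The cost is one SAP paragraph, a few lines in the program for the adverse event dataset, and possibly one extra row or footnote in the treatment-emergent event tables. No new data are needed, because the end date is already collected. The change should be made before unblinding.

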18.1.2 Deaths and Serious Adverse Events

A listing of deaths and other serious AEs (SAE) will be provided by subject.

18.1.3 Laboratory Data

Clinical laboratory data will be presented using units from the study data tabulation model (SDTM) Controlled Terminology.

All laboratory data will be listed, including laboratory variables not listed in the protocol. A separate listing, including out-of-range values will also be provided. Normal ranges will be used directly from the clinical laboratory.

Descriptive statistics will be provided to summarize continuous laboratory results of clinical chemistry and hematology (observed and derived absolute changes from baseline) by treatment and scheduled time.

18.1.4 Vital Signs

All vital signs data (observed measurements and derived absolute changes from baseline) will be listed by subject for all timepoints.

Descriptive statistics will be provided to summarize vital signs (observed and changes from baseline) by treatment and scheduled time.

18.1.5 Electrocardiograms

The observed measurements and derived changes from baseline for all ECG parameters and any corresponding abnormalities will be listed by subject for all timepoints.

Descriptive statistics will be provided to summarize mean ECG parameters (observed and changes from baseline) by treatment and scheduled time.

Scatterplots will be presented with the time-matched individual QTcF (absolute and absolute change from baseline) value vs PK concentration (both analytes). Separate plots for absolute and change from baseline QTcF and separate plots for PK analytes, i.e. 4 plots in total.

18.1.6 Physical Examinations

The findings and changes from previous visits for physical examination will be listed.

18.1.7 Body Weight

The results of the body weight measurements will be listed. The results at screening are listed as demographic data, but will also be listed here for completeness.

18.1.8 C-SSRS

The results of the Columbia-Suicide Severity Rating Scale (C-SSRS) questionnaire will listed.

Appendix 1: Glossary of Abbreviations

Glossary of Abbreviations:	
AE	Adverse event
ADaM	Analysis data model
ANOVA	Analysis of variance
BMI	Body mass index
BQL	Below the quantifiable limit
CA	cinnamaldehyde
CDISC	Clinical Data Interchange Standard Consortium
CSR	Clinical study report
C-SSRS	Columbia-Suicide Severity Rating Scale
CV	Coefficient of variation
DBF	Dermal Blood flow
ECG	Electrocardiogram
eCRF	Electronic case report form
EDS	Early Development Services
ICH	The International Conference on Harmonization of Technical Requirements for Registration of Pharmaceuticals for Human Use
LDI	Laser doppler imaging
LLOQ	Lower limit of quantification
LSCI	Laser Speckle contrast imaging
LSMeans	Least Square Means
MedDRA	Medical Dictionary for Regulatory Activities
PD	Pharmacodynamic
PDAS	Pharmacodynamic Analysis Set
PK	Pharmacokinetic
PU	Perfusion units
QA'd	Quality assured
QC'd	Quality controlled
RAND	Randomized Analysis Set
SAF	Safety Analysis Set
SAP	Statistical analysis plan
SAE	Serious adverse event
SD	Standard deviation

SDTM	Study data tabulation model
TE	Treatment-emergent
TEAE	Treatment-emergent adverse event
TFL(s)	Tables, figures and listings
WHO-DDE	World Health Organization – Drug Dictionary Enhanced

Appendix 2: Schedule of Assessments

	S		Treatment Period 1				Treatment Period 2				Treatment Period 3				Treatment Period 4			FU	ED ^d	
Study Day	≤28		-1 ^b	1	2	8	14 ^b	15	16	22	28 ^b	29	30	36	42 ^b	43	44	50	-	
Visit Window (days)	-		-	-	-	±1	-	-	-	-	±1	-	-	-	±1	-	-	-	±2	-
Visit	1 ^a	2 ^a	3 ^c		4	5 ^c		6	7 ^c		8	9 ^c		10						
Admit to CRU			X				X				X				X					
Discharge from CRU					X			X				X			X			X		
CRU visit	X	X				X				X				X				X	X	
Informed consent	X																			
Medical history	X																			
Height	X																			
Weight	X		X															X	X	
Physical examination	C		D	D	D	D	D	D	D	D	D	D	D	D	D	D	D	C	C	
Urine drug screen and ethanol test	X		X				X				X				X			X	X	
Hematology and clinical chemistry	X			P	24h			P	24h			P	24h			P	24h	X	X	
Urinalysis ^e	X			P														X	X	
β-hCG pregnancy test	X		X			X	X			X	X				X	X		X	X	
C-SSRS	X		X				X				X				X			X	X	
Vital signs including temperature	X			P and 3h	24h			P and 3h	24h			P and 3h	24h			P and 3h	24h	X	X	
ECG ^f	X			P and 3h	24h			P and 3h	24h			P and 3h	24h			P and 3h	24h	X	X	
Randomization				X																
Study drug administration ^g				X				X				X					X			
PK blood sample ^h				P and 3h	24h	X		P and 3h	24h	X		P and 3h	24h	X		P and 3h	24h	X	X	
DBF by LDI ^{i,j}		X																		
DBF by LDI and LSCI ^j				P and 3h	24h			P and 3h	24h			P and 3h	24h			P and 3h	24h			
AE / Con Med	← X →																			

Abbreviations: AE = adverse events; C = compete physical examination; Con Med = concomitant medications CRU = clinical research unit; C-SSRS= Columbia-Suicide Severity Rating Scale; D = directed physical examination; DBF = dermal blood flow; ECG = electrocardiogram; ED = early discontinuation; FU = safety follow-up; h = hour; LSCI = laser speckle contrast imaging; LDI = laser Doppler imaging; P = pre-dose assessment; PK = pharmacokinetic; S = Screening.

Note: In the event that assessments are planned for the same time, assessments should be conducted in following order: LSCI DBF assessment, LDF DBF assessment, PK sample, and ECG/vital signs.

The PK sample should be collected as soon as the LDI/LSCI DBF assessment is completed. The ECG and vital signs measurement should be obtained at least 30 minutes after the PK sample is drawn.

- a Screening visits will be performed within 28 days before the administration of first dose. All participants will have 2 screening visits with the first to evaluate the health of the participant and the second visit to undergo the LDI DBF assessment.
- b Can be performed on a day prior to dosing or pre-dose on day of dosing.
- c All participants will remain in the CRU until completion of all procedures that occur the day following each dose.
- d Participants who discontinue the study prior to study completion will complete the ED visit procedures.
- e A standard urine dipstick may be used.
- f A single 12 lead ECGs will be obtained in the supine position after at least 10 minutes rest.
- g Study drug will be administered in a fasting state (8 hours pre-dose until 4 hours post-dose). The exact time study drug is administered will be recorded.
- h The timing of PK sample collections may be adjusted based on clinical needs. The exact sample collection dates and times must be recorded.
- i All participants will have an LDI and LSCI procedure with cinnamaldehyde challenge to measure DBF at stipulated time points. The pre-dose measurement will include at least 30 minutes of acclimatization, followed by a dermal blood flow measurement, without cinnamaldehyde application. Each post-dose measurements will include at least 30 minutes of acclimatization, followed by a pre-cinnamaldehyde dermal blood flow measurement (about 10 minutes before cinnamaldehyde application). Next, cinnamaldehyde will be applied and a post-cinnamaldehyde measurement at 20 minutes following the cinnamaldehyde application will be performed. The LDI assessment will be performed following completion of LSCI assessment.

Appendix 3: List of End of Text Outputs

TFLs listed below can also be used in the body of the CSR.

Output	Title	Analysis Set
Section 12.1 Demographic and Other Baseline Data		
Section 12.1.1 Demographic Data		
Listing 12.1.1.1	Subject Randomization and Treatment Assignment	RAND
Table 12.1.1.2	Summary of Subject Disposition	RAND
Table 12.1.1.3	Summary of Demographics (Safety Analysis Set)	SAF
Table 12.1.1.4	Summary of Demographics (PD Analysis Set) (This table may be combined with 12.1.1.3 if PDAS is equal to SAF)	PDAS
Listing 12.1.1.5	Subject Demographics	SAF
Listing 12.1.1.6	Analysis Sets	RAND
Section 12.1.1 Other Baseline Data		
Listing 12.1.2.1	Medical History	SAF
Listing 12.1.2.2	Prior and Concomitant Medications	SAF
Listing 12.1.2.3	Result of Serology Tests	SAF
Table 12.1.2.4	Result of Pregnancy Tests	SAF
Section 12.2 Compliance Data		
Listing 12.2.1	Study Dates	SAF
Listing 12.2.2	Subject Disposition	SAF
Listing 12.2.3	Study Drug Administration	SAF
Section 12.3 Safety Data		
Section 12.3.1 Adverse Events		
Table 12.3.1.1	Table of Deaths and Other Serious Adverse Events	SAF
Listing 12.3.1.2	Adverse Events Leading to Withdrawal	SAF
Listing 12.3.1.3	Adverse Events	SAF
Table 12.3.1.4	Summary of All Treatment-Emergent Adverse Events by System Organ Class and Preferred Term	SAF
Table 12.3.1.5	Summary of Related Treatment-Emergent Adverse Events by System Organ Class and Preferred Term	SAF
Table 12.3.1.6	Summary of Treatment-Emergent Adverse Events by Treatment, Relationship and Severity	SAF
Section 12.3.2 Clinical Laboratory		
Listing 12.3.2.1	Clinical Laboratory Results - Chemistry	SAF
Listing 12.3.2.2	Clinical Laboratory Results - Hematology	SAF

Listing 12.3.2.3	Clinical Laboratory Results - Urinalysis	SAF
Listing 12.3.2.4	Clinical Laboratory Results - Alcohol and Drug Screen Test Results	SAF
Listing 12.3.2.5	Clinical Laboratory Results - Comments	SAF
Table 12.3.2.6	Summary of Clinical Laboratory Data - Clinical Chemistry	SAF
Table 12.3.2.7	Summary of Clinical Laboratory Data - Hematology	SAF
Table 12.3.2.8	Listing of Abnormal Laboratory Values	SAF

Section 12.3.3 Vital Signs Data

Listing 12.3.3.1	Vital Signs	SAF
Table 12.3.3.2	Summary of Vital Signs	SAF

Section 12.3.4 ECG Data

Listing 12.3.4.1	12-Lead Electrocardiogram Results - Individual Parameters	SAF
Listing 12.3.4.2	Lead Electrocardiogram Results - Investigator's Interpretation and Specification of Abnormalities	SAF
Table 12.3.4.3	Summary of 12-Lead Electrocardiogram	SAF
Figure 12.3.4.4	QTcF vs LY3526318 and M6 Plasma Concentrations (absolute and change from baseline)	SAF

Section 12.3.5 Other Safety Data

Listing 12.3.5.1	Physical Examination Findings and Changes	SAF
Listing 12.3.5.2	Body Weight	SAF
Listing 12.3.5.3	C-SSRS Results	SAF

Section 12.4 Pharmacokinetic and Pharmacodynamic Data
Section 12.4.1 Plasma Pharmacokinetic Data

Listing 12.4.1.1	LY3526318 and M6 Plasma Concentrations, Sampling Time Deviations and Comments (by treatment and time point)	SAF
Table 12.4.1.2	Descriptive Statistics of LY3526318 Plasma Concentrations	SAF
Table 12.4.1.3	Descriptive Statistics of M6 Plasma Concentrations	SAF

Section 12.4.2 Plasma Pharmacodynamic Data

Listing 12.4.2.1	Individual LDI and LSCI Results and Time Deviations and Comments	SAF
Table 12.4.2.2	Descriptive Statistics of LDI-DBF	PDAS
Table 12.4.2.3	Descriptive Statistics of LSCI-DBF	PDAS
Table 12.4.2.4	Statistical Analysis (ANOVA) of LDI-DBF (% pre- to post-CA)	PDAS
Table 12.4.2.5	Statistical Analysis (ANOVA) of LSCI-DBF (% pre- to post-CA)	PDAS
Table 12.4.2.6	Statistical Analysis (ANOVA) of LDI-DBF (absolute value)	PDAS

Table 12.4.2.7	Statistical Analysis (ANOVA) of LSCI-DBF (absolute value)	PDAS
Figure 12.4.2.8	Arithmetic Mean (\pm SD) LDI-DBF versus Time on Linear Scale	PDAS
Figure 12.4.2.9	Arithmetic Mean (\pm SD) LSCI-DBF versus Time on Linear Scale	PDAS
Figure 12.4.2.10	Combined Individual LDI-DBF versus Time On Linear Scale	PDAS
Figure 12.4.2.11	Combined Individual LSCI-DBF versus Time On Linear Scale	PDAS
Figure 12.4.2.12	Individual LDI-BDF versus Time On Linear Scale	SAF
Figure 12.4.2.13	Individual LSCI-BDF versus Time On Linear Scale	SAF

